## 5.3 Endpoints

### 5.3.1 Efficacy endpoint

#### (1) Primary endpoints

- 1) Mean Hb at treatment period Weeks 20 and 24
- 2) Hb at each treatment period timepoint
- 3) Ratios of subjects with mean Hb within the target range (11.0–13.0 g/dL), <11.0 g/dL, and  $\geq 13.0$  g/dL at each timepoint in treatment period
- 4) Correction cohort only: Days from initiation of treatment period required to reach target Hb range (11.0–13.0 g/dL)
- 5) Correction cohort only: Rate of increase of Hb levels

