## 12. Withdrawal criteria and procedures

### 12.1 Withdrawal criteria

Subjects will be withdrawn from the study if the following criteria are met:

- (1) If the subject expresses a desire to withdraw from the study.
- (2) If it is discovered that the subject is clearly ineligible for study participation.
- (3) If investigators/subinvestigators determine that AEs make continued participation in the study difficult.
- (4) If investigators/subinvestigators determine that continuation of the study is inappropriate for a subject, such as if hyperviscosity syndrome occurs or if control of Hb within the target range is impossible.
- (5) If continuous haemodialysis is initiated, or if the subject receives a renal transplant.
- (6) If renal function recovers such that peritoneal dialysis is discontinued.
- (7) If pregnancy of the subject is discovered.
- (8) If the investigator/subinvestigator determines a subject should withdraw from the study for any other reason.

Rationale

- (1) Set out of ethical considerations.
- (2) (5) (6) Set in order to prevent study drug administration to subjects unsuitable for inclusion in safety or efficacy evaluation.
- (3) (4) (7) Set out of safety considerations.
- (8) Set in order to allow the investigator/subinvestigator to make determinations regarding study continuation for significant safety-related reasons other than those enumerated above.

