## **7.3 Handling of efficacy endpoints if rescue therapy is performed**

If rescue therapy is performed, data from the day after rescue therapy should not be used for efficacy analysis.

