#### 8.1.2 Descriptive statistics to calculate

Types of continuous variables to be calculated for each descriptive statistics item are provided below. Number of subjects, mean, standard deviation (SD), median, minimum, maximum, and 2-sided 95% CI of the mean.

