(3) Proportion of subjects with mean Hb value within the target range ( $\geq 11.0$  to  $< 13.0$  g/dL),  $< 11.0$  g/dL, and  $\geq 13.0$  g/dL at each evaluation time point in the treatment period

The number, proportion, and 95% CI (Clopper-Pearson [Exact] method) of subjects with Hb value within the target range (11.0 g/dL to  $< 13.0$  g/dL, within),  $< 11.0$  g/dL (below), and  $\geq 13.0$  g/dL (above) at each time point of the treatment period should be provided. The McNemar test shall be used to compare before and after achievement for each treatment category at the first day of the treatment period and evaluation time point.

The proportion of subjects in each Hb value category (within the target range [11.0 g/dL to  $< 13.0$  g/dL],  $< 11.0$  g/dL or  $\geq 13.0$  g/dL) at each evaluation time point of the treatment period should be provided as a stacked bar graph assuming that the number subjects at the evaluation time point is 100%. Stacked bar charts should be separately prepared.

(4) Number of days from the first day of the treatment period required to reach the target Hb value range ( $\geq 11.0$  g/dL to  $< 13.0$  g/dL)

Descriptive statistics should be calculated for number of days required from the first day to reach target Hb value range (11.0 g/dL to  $< 13.0$  g/dL) of the treatment period. The number of days should be calculated as the first evaluation date reached target Hb value range – first date of the treatment period

+ 1. If target Hb value range is not achieved, the final date of evaluations – first date of the treatment period + 1 will be assumed.

A Kaplan-Meier plot should be shown for days from the first day of the treatment period required to reach the target Hb value range.

No subjects with an Hb value of  $\geq 11.0$  g/dL on the first day of the treatment period will be included in the calculation.

Only the Conversion (Hb value  $< 11.0$  g/dL) cohort will be analyzed.

(5) Hb value increase rate

Descriptive statistics should be calculated for the Hb value increase rate (g/dL/week).

The Hb value increase rate should be analyzed by 2 methods defined in the “4.13 Hb value increase rate”.

Only the Conversion (Hb value  $< 11.0$  g/dL) cohort will be analyzed.

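### SAP 8.5.1(4) gives subjects who never reach the Hb target their last evaluation day as days to target and summarises it uncensored, so early leavers count as early successes

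*SAP*

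**What the plan says.** SAP 8.5.1(4) uses a single variable. For subjects who reach 11.0 to <13.0 g/dL, "The number of days should be calculated as the first evaluation date reached target Hb value range", minus the first treatment date, plus 1. For the rest, "If target Hb value range is not achieved, the final date of evaluations" takes the place of the attainment date in the same formula.

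That variable is then summarised: "Descriptive statistics should be calculated for number of days required from the first day to reach target Hb value range". SAP 8.1.2 defines the content for continuous variables: "Number of subjects, mean, standard deviation (SD), median, minimum, maximum, and 2-sided 95% CI of the mean". A plot is requested as well: "A Kaplan-Meier plot should be shown for days from the first day of the treatment period required to reach the target Hb value range". No Kaplan-Meier median, quartile, confidence interval or proportion is requested, and the section does not say who is an event and who is censored. The only subjects left out are those with Hb of at least 11.0 g/dL on the first treatment day. The errata to SAP Version 2 do not touch this rule.

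Two other provisions decide who gets a short assigned day. Protocol 12.1(4) allows withdrawal "such as if hyperviscosity syndrome occurs or if control of Hb within the target range is impossible". SAP 7.3 says that after rescue, "data from the day after rescue therapy should not be used for efficacy analysis", and SAP 8.5 repeats this for all efficacy analysis.

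On status, Protocol 5.3.1 lists the endpoint as primary but restricts it: "Correction cohort only: Days from initiation of treatment period required to reach target Hb range". SAP 3.1.1 does not list it, although SAP 8.5.1 analyses it under its primary-endpoint heading, in the Conversion (Hb <11.0 g/dL) cohort only.

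**The concern.** The last evaluation day of a subject who has not reached target is a lower bound on the time to target. It is the right censoring time for a Kaplan-Meier curve. A mean, SD, median or confidence interval of the mean cannot carry a bound, so each of them treats it as an observed attainment day.

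The rule then rewards early failure. A subject withdrawn early because Hb could not be controlled, or rescued early, can receive one of the shortest times in the cohort. The bias favours the drug, and the numerical summary can disagree with the curve beside it. Under SAP Section 6 and the errata the Correction cohort (two subjects) gets only individual Hb plots, so this is the trial's only time-to-target result.

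**Working it through.** **The plan's own figure.** The documents give no figure for days to target. The only computed design figure is the precision of mean Hb (Protocol 6.1, SAP 2.3): n = 40, SD 1.78, half-width = t(0.975, 39) × 1.78/√40 = 0.569. This reproduces the stated ±0.57 g/dL and is not affected by this point.

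**Inputs from the documents.** Hb visits fall at Weeks 2, 4, 6, 8, 10, 12, 16, 20 and 24 (Protocol 9.1). With the SAP's +1 these are Days 15, 29, 43, 57, 71, 85, 113, 141 and 169. The size of the Conversion (Hb <11.0 g/dL) cohort and the dropout, rescue and response rates are not given. All values for them below are assumptions.

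**Effect of one subject.** Take someone last evaluated on Day L who would not have reached target by Day 169. The assigned value is L. In a mean capped at the end of follow-up it should be 169. The mean falls by (169 − L)/n. For L = 29 this is 140/n: 14.0 days at n = 10, 7.0 at n = 20, 5.6 at n = 25. A non-reacher who completes Week 24 gets about Day 169 and causes no shortfall against the capped mean.

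**Worked example (assumed, n = 20).** Ten reach target: 4 on Day 29, 4 on Day 57, 2 on Day 85. Their days sum to 116 + 228 + 170 = 514. Only the fate of the ten non-reachers changes:

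- All ten stay to Day 169: mean (514 + 1,690)/20 = 110.2; median (85 + 169)/2 = 127.
- Six leave on Day 15 and four stay: mean (514 + 90 + 676)/20 = 64.0; median (29 + 57)/2 = 43. The summary improves by 46.2 days in the mean with no additional success.
- Three leave on Day 15, three on Day 29 and four stay: mean (514 + 45 + 87 + 676)/20 = 66.1; median 43.

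For the third case with non-reachers censored, the Kaplan-Meier proportion not yet at target is 13/17 = 0.765 after Day 29, 0.765 × 6/10 = 0.459 after Day 57, and 0.459 × 4/6 = 0.306 after Day 85. The median is 57 days. The mean restricted to Day 169 is 29 + 28 × 0.765 + 28 × 0.459 + 84 × 0.306 = 89.0 days. The table would show 66.1 and 43 beside a curve whose median is 57.

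**Simulation.** Exponential time to target, dropout unrelated to response, 200,000 subjects per scenario. Cells give the SAP mean / true mean capped at Day 169.

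| Dropout by Week 24 | True median 42 d | True median 84 d | True median 140 d |
|---|---|---|---|
| 0% | 66.0 / 66.0 | 99.2 / 99.2 | 120.7 / 120.7 |
| 10% | 63.7 / 66.0 | 94.7 / 99.2 | 114.7 / 120.7 |
| 20% | 61.1 / 66.0 | 89.7 / 98.9 | 108.4 / 120.6 |
| 30% | 58.7 / 66.2 | 84.9 / 99.2 | 101.8 / 120.8 |
| 40% | 55.8 / 66.2 | 79.7 / 99.1 | 94.6 / 120.4 |

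The shortfall is nil without dropout, 2.3 to 6.0 days at 10%, and 10.4 to 25.8 at 40%. The Kaplan-Meier restricted mean matches the true value in every scenario.

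A second model (lognormal, log-SD 0.7, latent median 56 to 112 days, 10 to 20% never reaching) gave 2.7–5.4, 5.5–11.0, 8.6–16.8 and 11.7–23.3 days at 10, 20, 30 and 40% dropout. A separate run of this model gave about 3–6 at 10% and 13–24 at 40%. The exact figure depends on where a leaver's last evaluation falls between visits. In this model the SAP median was 0 to 42 days below the Kaplan-Meier median.

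**The case against.** The strongest reply is that the rule is simply the Kaplan-Meier censoring time, loosely worded in translation. The assigned day is the usual censoring day and a Kaplan-Meier plot follows. The SAP's lists of output tables and figures (Sections 11 and 12) are not in the text available here and might define censoring. That possibility remains open. But the rule directly follows the request for descriptive statistics, comes before the plot is mentioned, and speaks of an assumed value. A programmer following Section 8.5.1(4) would put these days into the mean.

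On rescue, the section says final evaluation, not final usable evaluation. If the date were not cut at rescue, a rescued non-reacher who completes would get about Day 169 and do no harm. SAP 7.3 and 8.5 nevertheless bar later data from every efficacy analysis, so the cut is the better reading. It is fair that the criteria-based ESA route is unlikely by Day 29: with a first increase at Week 2 and the next at Week 6, two weeks at maximum dose ends near Day 57, where the effect is (169 − 57)/n = 5.6 days at n = 20. Discretionary rescue, transfusion and withdrawal can come earlier.

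The size is assumed throughout, and 40% dropout has no basis in the documents. Entry Hb of at least 9.0 g/dL makes faster attainment plausible. With a latent median of 28 days and 10% never reaching, the shortfall is only 1.6–1.8 days at 10% dropout and 3.3–3.7 at 20%. Part of the gap in medians reflects visits 14 to 28 days apart, and some scenarios show none.

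The stakes are also low. No test or decision depends on the result, and non-response stays visible in the proportions by Hb category, the rescue proportions and the discontinuation reasons. This limits the importance but does not make the statistic correct.

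**Conclusion.** The concern holds. As written, SAP 8.5.1(4) puts uncensored last-evaluation days into the only numerical summary of time to target. The mean is then too short whenever a subject's usable follow-up ends early before a target they would have reached later or not at all; the median can be too short as well.

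The direction and the per-subject effect, (169 − L)/n, are arithmetic. The overall size is conditional: nil without early leavers, a few days at 10% dropout, and between 10 and 26 days at 40%, under the assumed response times of the two main models.

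The point should be fixed, but it does not threaten the trial's main conclusion. The item is descriptive, confined to one subcohort of a 40-subject single-arm study, and absent from SAP 3.1.1. The analysis of mean Hb at Weeks 20 and 24 is unaffected.

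**What to change.** In SAP 8.5.1(4):

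- State that attaining 11.0 to <13.0 g/dL is the event. Subjects who do not attain it are censored at their last usable Hb evaluation, which for rescued subjects is no later than the day of rescue, in line with SAP 7.3. Use that day only as a censoring time.
- Replace the plain descriptive statistics with the Kaplan-Meier median and quartiles with 95% CI, and the number and Kaplan-Meier proportion reaching target by Weeks 4, 8, 12 and 24.
- Report the number censored before Week 24 by reason. Kaplan-Meier is itself somewhat optimistic if non-responders leave more often. With never-reachers leaving at 5 times the hazard (latent median 80 days, 20% never reaching, 20% dropout overall), it gave 0.73 reaching target by Week 24 against a true 0.69.
- Do not replace the summary with a mean among reachers only. In the worked example that is 514/10 = 51.4 days, shorter still.

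Protocol 13.3.2 also asks for descriptive statistics of this variable, so SAP Section 9 should record the departure and its reason, as Protocol 13.4 requires.

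The cost is wording and one small change of output, since the Kaplan-Meier analysis is already planned and the same procedure gives the quantiles. If tables already exist, the new figures can be added from the same data and the plain mean and median labelled as uncensored. The reported time may look less favourable, and a quantile may not be estimable. With an assumed n = 20, latent median 80 days, 20% never reaching and 20% dropout, the median was not estimable in about 5% of simulated trials.

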#### 13.3.2 Efficacy

(1) Analysis methods for primary endpoint

1) Mean Hb of treatment period Weeks 20 and 24

To determine mean Hb (mean at treatment period Weeks 20 and 24), mean Hb at each timepoint will be modeled using MMRM with the following model, and mean Hb at treatment period Weeks 20 and 24 and their two-sided 95% CI will be calculated.

[MMRM model]

- Fixed effects: Evaluation period, patient cohort (correction or conversion cohort), interactions of evaluation period × patient cohort (correction or conversion cohort)
- Random effects: Subjects

2) Hb at each treatment period timepoint

Descriptive statistics will be calculated for Hb level at each treatment period timepoint,

and analysis performed taking into account changes over time using MMRM.

- 3) Ratios of subjects with mean Hb within the target range (11.0–13.0 g/dL), <11.0 g/dL, and  $\geq$ 13.0 g/dL at each timepoint in treatment period

Numbers and ratios of subjects with mean Hb at each treatment period timepoint within the target range (11.0–13.0 g/dL), <11.0 g/dL, and >13.0 g/dL will be shown.

- 4) Correction cohort only: Days from the first day of the treatment period required to reach target Hb range (11.0–13.0 g/dL)

Descriptive statistics will be calculated for days from the first day of the treatment period required to reach target Hb range (11.0–13.0 g/dL). A Kaplan-Meier plot will be shown for days from the first day of the treatment period required to reach target Hb range (11.0–13.0 g/dL). Statistical summaries will not include subjects with Hb of  $\geq$ 11.0 g/dL on the first day of the treatment period.

- 5) Correction cohort only: Rate of increase of Hb levels

Descriptive statistics will be calculated for rate of Hb increase.

- (2) Analysis methods for other endpoints

Incidence and ratios will be shown for discrete data, while descriptive statistics will be calculated for continuous data.

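### The Kaplan-Meier plot of days to target Hb has no event or censoring rule, and on its natural reading it censors rescued subjects and those withdrawn for uncontrolled Hb as if they could still reach target at the usual rate

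*SAP*

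**What the plan says.** SAP 8.5.1 (4) measures days from the first treatment day to the first evaluation in the target range. It is confined to the Conversion (Hb <11.0 g/dL) cohort, without subjects at 11.0 g/dL or above on the first day. It asks for descriptive statistics and a plot: "A Kaplan-Meier plot should be shown for days from the first day of the treatment period required to reach the target Hb value range". For the rest there is one rule, whatever the reason: "If target Hb value range is not achieved, the final date of evaluations" minus the first date plus one is used. The section does not say whether that date enters the curve as an event or as a censored time.

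Three other rules bear on it:

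- SAP 7.3, repeated in SAP 8.5: "data from the day after rescue therapy should not be used for efficacy analysis". Protocol 13.2 (3) likewise excludes data after rescue.
- Protocol 12.1 (4) lets the investigator withdraw a subject "if control of Hb within the target range is impossible".
- Protocol 8.5.3 lets rescued subjects stay in the study.

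SAP 8.5.4.2 refers dropout to SAP section 7, which covers MMRM and LOCF but has no time-to-event or competing-event rule. Protocol 13.3.2 plans the same display for the Correction cohort ("A Kaplan-Meier plot will be shown for days from the first day of the treatment period required to reach target Hb range"), also without a censoring rule. Those Correction cohort analyses were later dropped (SAP section 6 and the errata), so the SAP version is the one that matters.

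**The concern.** Once a subject is rescued, no later Hb counts, so under the plan's own rules the endpoint can no longer be reached. A subject withdrawn because Hb cannot be controlled in target has left because of the outcome. Kaplan-Meier gives a censored subject the same later hazard as those still at risk, which is not credible for the second group and has no meaning for the first. Both are competing events. If they are censored, one minus Kaplan-Meier can never lie below the cumulative incidence, and it lies above it whenever such an exit comes before a later target event.

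In a single-arm trial this curve is the only planned display of the cumulative share brought to target over time, and it is likely to be read that way. In the extreme, if everyone who remains reaches target, the curve ends at 100% however many were rescued.

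**Working it through.** **The plan's own figure.** The only design figure is the precision of mean Hb: t(0.975, 39) × 1.78/√40 = 2.023 × 0.2814 = 0.569, which reproduces ±0.57 g/dL. It has no bearing on this analysis, for which the plan states no figure.

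**Inputs.** The documents give no cohort size, rescue rate, withdrawal rate or attainment rate. All values below are assumptions.

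**Hand example.** Take N = 20, of whom E = 12 are seen to reach target: 1, 2, 2, 2, 1, 1, 1, 1, 1 at Weeks 2, 4, 6, 8, 10, 12, 16, 20, 24. Let f subjects exit for failure just after a visit by which m have reached target, with no other early censoring. The Kaplan-Meier product telescopes:

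- 1−KM at Week 24 = 1 − [(N−m)/N] × [(N−E−f)/(N−m−f)]
- cumulative incidence with the exits as competing events = E/N = 12/20 = 60.0%

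With f = 2 just after Week 8 (m = 7): 1 − (13/20) × (6/11) = 64.5%, an excess of 4.5 points. In the same way:

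| Exits f | after Week 4 (m = 3) | after Week 8 (m = 7) | after Week 16 (m = 10) |
|---|---|---|---|
| 0 | 60.0% | 60.0% | 60.0% |
| 1 (5%) | 62.8% | 62.1% | 61.1% |
| 2 (10%) | 66.0% | 64.5% | 62.5% |
| 3 (15%) | 69.6% | 67.5% | 64.3% |

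If all exits follow the last target event, the result is again 60.0%.

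**General form.** Let p be the share who exit, a the share of the others who reach target by Week 24, and u the share of those achievers who have done so before the exits. Then

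- 1−KM = 1 − [1−(1−p)au] × (1−a)/(1−au)
- cumulative incidence = (1−p)a
- excess = p·a·(1−u)/(1−a·u)

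The excess is zero when p = 0 or u = 1. With u = 0.5:

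| p | a = 80% | a = 95% |
|---|---|---|
| 5% | 0.05×0.80×0.5/0.600 = 3.3 points | 0.05×0.95×0.5/0.525 = 4.5 points |
| 10% | 6.7 points | 9.0 points |
| 15% | 10.0 points | 13.6 points |

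Simulated trials with 15 or 20 subjects, the same p and a, and exits at Weeks 4 to 16 gave 3 to 4, 6 to 8 and 9 to 12 points. A second set gave 3 to 5, 6 to 9 and 10 to 14.

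**Against the noise.** For n = 20, p = 10%, a = 95%, the simulated averages were 1−KM 0.933 and cumulative incidence 0.856. SE = √(0.856×0.144/20) = 0.079, so the excess of 0.077 is about one standard error. Across the first set of simulations the excess was 0.3 to 1.3 standard errors.

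**Other reading of the date rule.** If the final evaluation of a rescued subject is the last study visit, that subject stays at risk to the end. In the hand example, if all exits are rescues of this kind, the curve ends at 60.0%. Only withdrawals then add to the excess.

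**The case against.** The strongest reply is that the plan never says these subjects are censored. SAP 8.5.1 (4) uses neither term, SAP 7.3 drops data without setting a censoring date, and a rescued subject who continues has later study visits. This stands: censoring at rescue is an inference. It is the reading most consistent with SAP 7.3, since a visit whose Hb may not be used is a poor candidate for the final efficacy evaluation. Withdrawn subjects end early on either reading.

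A reader might go further, and three stronger readings are not supported:

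- That the share is certainly overstated. The excess needs at least one such exit before a later target event, and Protocol 3.3 (5) screens out patients likely to need immediate rescue.
- That Kaplan-Meier assumes each failure will reach target. It assumes only the same later hazard.
- That every rescue is a low-Hb failure. Phlebotomy is for high or fast-rising Hb, and Protocol 12.1 (4) also names hyperviscosity. Phlebotomy before target still ends countable follow-up under SAP 7.3.

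The weight is also limited. The SAP asks for a plot in a subset, with no Kaplan-Meier estimate, interval or test, and SAP 3.1.1 does not list days to target as a primary endpoint. Failures would show elsewhere: rescue proportions (SAP 8.5.2 (3)), discontinuation reasons (SAP 8.2.2), individual Hb courses (SAP 8.5.1 (2)) and target-range proportions by visit (SAP 8.5.1 (3)). All of this stands. The by-visit proportions do not repair the curve, however. They give status at a visit, and the stacked bars take subjects present at that visit as 100%, so those who left disappear there too.

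**Conclusion.** The concern holds in conditional form. The plan leaves event and censoring undefined, and its rules taken together most naturally censor subjects who can no longer reach the endpoint or who left because of it. On that reading the direction of any bias is known: upward, or nil. Its size is not known. Under the assumed 15 to 20 subjects, 5% to 15% such exits at Weeks 4 to 16, and 80% to 95% of the others reaching target, the excess is about 3 to 12 points, and up to about 14 depending on when the exits fall. It is smaller when fewer subjects reach target (1.1 to 9.6 points in the hand example) and zero with no such exits. If rescued subjects are kept at risk to their last study visit, only withdrawals contribute.

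This affects one supporting display in a subset, so it is an inexpensive improvement and not a threat to the trial's main conclusion. The descriptive statistics use the same dates but are a separate matter.

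**What to change.** In SAP 8.5.1 (4):

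1. Define the event as the first evaluation in the target range, and define the censoring date. State that for rescued subjects the final evaluation is the last one up to the day of rescue.
2. Show a cumulative incidence (Aalen-Johansen) curve. Before target, treat first rescue therapy of any type, death, and withdrawal for uncontrolled Hb as competing events. Keeping these subjects as non-achievers to Week 24 gives the same curve if nobody leaves early for other reasons.
3. Report the cumulative incidence at Weeks 12 and 24 with 95% CI.
4. Keep the Kaplan-Meier plot as supportive.
5. As a sensitivity analysis, also treat other withdrawals (adverse event, transplant, haemodialysis) as competing events.

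This changes only the analysis; the rescue and withdrawal rules are untouched. No new data are needed: rescue details (Protocol 8.5.3), durations of concomitant treatments (8.5.4) and withdrawal dates and reasons (12.2) are already in the CRF. The programming is an event-code option in SAS PROC LIFETEST. The cost is a little wording and programming, and a displayed share that may be lower. If data are already locked, Protocol 13.4 requires the reason to be given and the result to be kept apart from the original plan.
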